1.3.9 Criteria for discontinuation

Patients have the right to withdraw from the trial at any time on their own request for any reason; the reason for withdrawal will be recorded in detail. Subjects wishing to discontinue their LNG-IUS while enrolled in the study will terminate their participation with the study as of IUS removal. These subjects will be asked to complete the final online study survey prior to IUS removal to review bleeding profiles and satisfaction questions. No further data will be obtained from the patient once withdrawal occurs. Any data obtained up to this point will be analyzed in accordance with intention to treat.

We will have close contact with participants through the daily electronic bleeding diary. Failure to respond to the bleeding diary for three consecutive days will prompt a phone call from the study coordinator to inquire about technological difficulties versus disinterest in the study. If we are unable to reach a subject by phone, email or letter over two weeks, their participation will be terminated. Likewise, subjects declining to return for the study visit or complete the final survey will be discontinued from the study. Any data obtained up to this point will be analyzed in accordance with intention to treat.

If a subject becomes pregnant while participating in the study, her participation will be discontinued. She will be asked to come in for a study visit with the investigator. Her study medication will be unblinded and she will receive counseling from the investigator on how to seek medical care.

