Between IUS insertion and study visit 1 (occurring 14-21 days after insertion), baseline bleeding with the LNG-IUS will be prospectively collected using bleeding diaries. This data will be used later as a covariate in analysis. A co-investigator (ob/gyn physician) will call each subject after at least 12 days of bleeding data collection to review exclusion criteria and to schedule study visit 1 if appropriate, as described in section 1.3.4. Subjects reporting concerns with their IUS will be referred to their primary provider or scheduled for a triage visit in family planning clinic to be examined by a physician as clinically indicated.

At study visit 1, bleeding diaries will be reviewed, and VAS scales (0-100mm) will be completed to obtain baseline assessment of bleeding satisfaction with the LNG-IUS. Each subject will receive one bottle of their assigned medication. Participants will be instructed to begin use of the study medication on day 21 after the insertion of their LNG-IUS and continue to take a twice daily oral dose of 10 mg for seven days. Estimated time to complete this visit is 15 minutes. Participants will receive a single text message or email reminder on the day they are due to start study medication. There will not be any specimens collected at this visit and there will be no results to share with subjects.

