A second message will be sent one minute after the first to inquire whether subjects took the study medication that day. If the subject does not respond to the text or email messages, a second set of texts or emails (2) will be sent the following morning. The subject has only these two chances to report their bleeding information for that day, and otherwise must use the paper diary. Responses to the messaging system will be compiled in a secured web database by Mir3, which can be accessed by research staff for data retrieval and entry onto research computers. Paper diaries will also be provided for use in case of technical difficulty in receiving or responding to text or email messages. Subjects are encouraged to complete paper diaries in addition to the electronic diary.

Follow up visits

Thirty days after initiating study drug, participants will receive an email with a link to a final study online survey via REDCap (attached). This survey will include questions assessing side effects, adverse events, and bleeding and IUS satisfaction. The satisfaction questions will utilize an electronic 100-mm visual analog scale. This study survey should take approximately 5-10 minutes to complete. Subjects not returning the survey within 7 days will be contacted by phone, text or email (based on stated contact preferences) and reminded to reply.

Compensation

Subjects will be compensated \$10 at enrollment and \$30 at the first study visit, which totals \$40. Additionally, subjects will be provided with compensation for completing the electronic bleeding diaries after use of study drug. Subjects will receive an additional \$1 each day that they respond to the electronic messages (up to 30 days total) and \$20 for completing the final survey. This is a total of up to \$50 that they can earn from completing the diaries and completing the study. The total compensation per subject is a maximum of \$90. Compensation will be loaded onto a debit card, which participants will receive at the enrolment visit.

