1.3.11 Data analysis

Data will be extracted and entered into STATA on a password-protected computer. Analysis will be performed with the blinded data. P value of 0.05 defines statistical significance. Randomization will be assessed and if there is imbalance found between treatment and placebo groups, regression analyses will be completed to accommodate these differences.

Primary objectives: The primary measurement for this study will be the mean number of bleeding or spotting (b/s) days experienced by participants in the treatment group compared to placebo group over 30 days after treatment initiation. We will record baseline data on b/s days in the 21-day run-in period to confirm that the randomization was successful in allotting women with equivalent baseline b/s days to each group. Each day, subjects will indicate via numeric coded text or email message response whether they had spotting, bleeding, or none. From these diaries, counts of total bleeding/spotting days will be obtained. Other secondary bleeding outcomes will be examined including number of bleeding/spotting episodes, the number of prolonged bleeding episodes (>8 days), and the longest bleeding-free interval. Comparisons between groups will be made using an independent sample two sided t-test. Data will be analyzed in an intention-to-treat fashion. If data are very skewed, non-parametric methods will be used to compare groups.

Secondary objectives:

1. Satisfaction and side effects

At the study visit and in the final survey, subjects will answer questions regarding their satisfaction with the IUS and their bleeding patterns, acceptability of bleeding, as well as side effects and adverse events. Satisfaction responses will be quantified using a visual analog scale between 0-100mm. Discontinuation from the study and discontinuation of the IUS during the study will be monitored as markers of dissatisfaction. Comparison of means between tamoxifen and placebo groups will be made using two sided t-tests, and side effects will be reported descriptively.

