1.6 Main problems anticipated

Recruitment: The family planning clinic at OHSU provides insertion of approximately 3-5 LNG-IUS devices per week. Additional insertions occur in the resident and generalist clinics. By targeting eligible women at clinic visits and by minimizing follow up procedures, we anticipate that recruitment will be feasible to complete within six months.

Retention: The short duration of the study and minimal follow up procedures should maximize retention. Similar prior studies in the LNG-IUS had low dropout rates, all with <20% loss to follow up (16,26,27). The proposed project is shorter duration (51 days total), which should decrease dropout even further. Nevertheless, our sample size was designed to account for a 20% dropout rate due to this risk of poor retention in women experiencing ongoing bleeding. Details on how we will manage loss to follow up are included in section 1.3.7.

Bleeding diaries: The text or email message bleeding diary through Mir3 has been utilized in similar studies with excellent response rates. However, a portion of participants in older studies had difficulty receiving or responding to text messages due to incompatible cell phone technology. Subjects who have difficulty receiving or responding to daily text messages can opt to receive identical email study survey messages instead and will have a paper diary to use as backup, which will utilize the exact same question and response categories.

Any unanticipated problems will be addressed by the PI and study co-investigators, with changes to the protocol as needed. Unanticipated problems could include medication side

effects or pregnancy in a study subject. Any pregnancy occurring during the study will be considered a serious adverse event and will prompt review of the study protocol and possible study discontinuation of the study.

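### Women who withdraw before day 30 with the IUS in place have no scheduled post-dose satisfaction score and no solicited side-effect list

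*Combined protocol and SAP*

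**What the plan says.** - **When the outcomes are asked.** Section 1.3.7 sets one survey after dosing: "Thirty days after initiating study drug, participants will receive an email with a link to a final study online survey via REDCap". On its content: "This survey will include questions assessing side effects, adverse events, and bleeding and IUS satisfaction". Women who have not returned it within 7 days are reminded.
- **The other time point.** Section 1.3.11 says "At the study visit and in the final survey, subjects will answer questions regarding their satisfaction with the IUS and their bleeding patterns". That visit precedes treatment. Section 1.3.6 reads "Between IUS insertion and study visit 1 (occurring 14-21 days after insertion), baseline bleeding with the LNG-IUS will be prospectively collected", and the tablets are handed out at that visit for a start on day 21. Its VAS score is a baseline.
- **Daily messages.** Section 1.3.7 and Appendix B ask about bleeding and tablet intake, and nothing else.
- **Women who leave.** Section 1.3.9 says of women having the IUS removed: "These subjects will be asked to complete the final online study survey prior to IUS removal to review bleeding profiles and satisfaction questions". It continues: "No further data will be obtained from the patient once withdrawal occurs". For other withdrawals the reason is documented. A woman who becomes pregnant is invited to an investigator visit. Neither is asked for the survey.
- **Analysis.** Section 1.3.11 says "Comparison of means between tamoxifen and placebo groups will be made using two sided t-tests, and side effects will be reported descriptively". No method for missing VAS scores is given.

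**The concern.** The protocol expects leaving to be related to the outcome. Section 1.3.11 uses study discontinuation as a marker of dissatisfaction. Section 1.6 justifies the 20% dropout allowance by poor retention among women who keep bleeding. Missing satisfaction scores would therefore tend to come from the less satisfied.

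Leaving may also differ by arm. Section 1.1.1 reports 2 versus 9 discontinuations for bleeding in the earlier tamoxifen trial. Those were implant users, and the protocol does not say whether they left the study or had the device removed, so this is only a hint.

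Section 1.3.9 promises intention-to-treat analysis of whatever was collected before a woman left. For a leaver who was not surveyed, that is a baseline VAS at most, so she cannot enter a t-test of post-dose means. For side effects, women who stay are prompted and these leavers are not, so ascertainment is uneven. Secondary objectives 2 (satisfaction) and 4 (side effects) are at stake. The primary bleeding comparison is a separate matter.

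**Working it through.** **1. The plan's own figure.** Section 1.3.2 gives 42 women, 21 per arm, from a 7-day difference, SD 7, 80% power, alpha 0.05 and 20% dropout.
- Normal approximation: 2 x (1.96 + 0.84)^2 x (7/7)^2 = 15.7, so 16 per arm; 16/0.8 = 20, total 40.
- t-test: 16.7, so 17 per arm; 17 x 1.2 = 20.4, so 21 (total 42), or 17/0.8 = 21.25, so 22 (total 44).

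All are within 2 women of 42. The figure is reproduced and is used below only for 21 per arm and 20%.

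**2. Who is asked for the survey.**

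| Group | Final survey | Other record |
|---|---|---|
| Stays to day 30 (including a woman who only stops the tablets) | Yes, with reminder | Self-reported adverse events |
| IUS removed before day 30 | Yes, before removal | IUS discontinuation counted |
| Withdraws before day 30, IUS in place | Not asked | Reason documented; study discontinuation counted; adverse events already reported |
| Terminated as unreachable before day 30 | Not asked | Study discontinuation counted; adverse events already reported |
| Discontinued for pregnancy | Not asked | Investigator visit |

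The third row is the main gap.

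**3. How many.** 0.20 x 21 = 4.2, about 4 per arm; 0.20 x 42 = 8.4, about 8 in all. This is a ceiling: the allowance is not split by reason and may include IUS removers, who are asked. The range used is 0 to 4 per arm.

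**4. Satisfaction in one arm.** Assume survey completers average 60 mm and k leavers of 21 would have scored between 20 and 60 mm. The mean over all 21 is ((21 - k) x 60 + k x leaver score)/21.

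| k | Leavers at 20 mm | Leavers at 60 mm | Completers' mean too high by |
|---|---|---|---|
| 1 | 1220/21 = 58.1 | 60 | 0 to 1.9 mm |
| 2 | 1180/21 = 56.2 | 60 | 0 to 3.8 mm |
| 4 | 1100/21 = 52.4 | 60 | 0 to 7.6 mm |

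**5. Satisfaction between arms.** With the same gap g between completers and leavers in both arms, the bias in the difference is g x (placebo leavers - tamoxifen leavers)/21. With an assumed g = 30 mm and 4 versus 2 leavers, it is 30 x 2/21 = 2.9 mm, towards no effect if tamoxifen improves satisfaction. Equal numbers leaving give zero.

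**6. Side effects, if taken from the survey alone.** Assume 4 true cases of 21 (19%), close to the headache figure of up to 20% in section 1.3.5.
- All k leavers are cases: 3/20 = 15%, 2/19 = 10.5%, 0/17 = 0% for k = 1, 2, 4.
- No leaver is a case: 4/20 = 20%, 4/19 = 21.1%, 4/17 = 23.5%.

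The range lies on both sides of 19%, so it shows uncertainty and not a direction. Events reported outside the survey would narrow it.

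**The case against.** **Side effects have other routes.** A reader might infer that side effects are recorded nowhere but the survey, and that leavers vanish from both outcomes. The documents do not support that. Objective 4 tracks self-reported adverse events, section 1.3.10 sends reported events to the principal investigator for review, and section 1.3.9 documents why a woman withdraws. A woman who leaves because of a side effect should be on record. Leavers also count in the discontinuation measure of dissatisfaction. This stands, and it confines the gap to the VAS score and the solicited list. None of these routes supplies a VAS score, and section 1.3.11 does not say how events reported outside the survey enter the descriptive summary.

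**Removers are fully covered.** One might read their exit survey as limited to bleeding and satisfaction. It is the same final survey, which section 1.3.7 says also covers side effects and adverse events.

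**Few women lost to contact are affected.** Three silent days trigger a call, and termination follows two weeks of failed contact, about 17 days in all. Since 30 - 17 = 13, a woman who goes silent after about day 13 from first dose is still due the survey. Those terminated sooner could seldom be reached anyway. This stands.

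**The effect is small.** With an assumed VAS SD of 20 to 30 mm and 17 versus 19 completers, the standard error is SD x sqrt(1/17 + 1/19) = 6.7 to 10.0 mm, so 2.9 mm is under half of one standard error. This is fair for that scenario. The SD, the split of leavers and the gap are all assumed.

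**Not everything can be seen.** The survey and the institution's reporting policy are not in the documents, so the survey items and the full adverse-event procedure cannot be checked.

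**Conclusion.** The gap is real and narrow. Women who withdraw before day 30 with the IUS in place have no scheduled post-dose VAS score and no solicited side-effect list, because of a stated rule and not merely a missing detail. The satisfaction part is the firmer one; for side effects, the loss is even ascertainment and not all knowledge of events.

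The size is unknown. At most about 4 of 21 women per arm are affected, if all of the planned 20% dropout left this way. The corresponding shift of 0 to 7.6 mm in one arm rests on assumed scores, and the between-arm bias depends on how leaving differs by arm. Section 1.6 expects dropout below that of earlier studies, so the true number may be smaller.

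A reader might also see a conflict over pregnancy, since section 1.6 says "Any pregnancy occurring during the study will be considered a serious adverse event and will prompt review of the study protocol" while data collection stops at IUS removal. There is none: section 1.6 concerns pregnancy during the study, and section 1.3.9 ends participation when the device is removed.

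**What to change.** - **Section 1.3.9, exit survey.** Ask every woman who withdraws or is discontinued after starting study drug, for any reason and whether or not the IUS is removed, to complete the existing REDCap final survey at exit if she agrees. Record its date.
- **Section 1.3.9, data after withdrawal.** Limit the bar on further data to what would come after that exit survey, or to women who refuse it.
- **Section 1.3.11.** State that adverse events and withdrawal reasons reported outside the survey are included in the descriptive side-effect summary.

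**Cost.** A short amendment and a few extra requests for a survey of 5 to 10 minutes, at most about 8 women in all, possibly with the existing $20 payment. Exit scores would be taken earlier than day 30, as already happens for IUS removers, which is why the date matters. Women who cannot be reached would gain little.

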One study examined the selective estrogen receptor modulator (SERM) tamoxifen to reduce bleeding days in users of a LNG contraceptive implant who complained of vaginal bleeding irregularities (2). Women were randomized to receive 10mg of tamoxifen or placebo twice daily for 10 days and were followed for 90 days. Women taking tamoxifen had significantly fewer days of bleeding and spotting than placebo over the first two months after dosing (6.24 vs 12.29 days in month one, $p=0.0003$; 6.78 v 11.87 days in month two, $p=0.0008$). The effect waned by the third month. This is the only treatment for progestin-induced bleeding which has shown a sustained bleeding reduction that lasted beyond the treatment period (18). Bleeding stopped within 7 days of starting the medication for 82% of tamoxifen users (compared to 56% of placebo, $p=0.005$). Women reported a higher level of satisfaction with tamoxifen compared to placebo, there were fewer discontinuations due to bleeding over the course of the study (2 vs 9), and side effects were minimal.

Exogenous progestins such as LNG cause decidualization of the endometrium with proliferation of fragile and thin walled vessels, which may be responsible for unscheduled bleeding (13,14). Tamoxifen is a mixed agonist-antagonist to estrogen and competitively inhibits estrogen binding at the estrogen receptor. Whether its effect is agonistic or antagonistic depends on the promoters present in each cell type (28,29). In the endometrium, tamoxifen acts as an antagonist to estrogen receptor beta cells, which may contribute to downregulation of endometrial angiogenesis, leading to decreased breakthrough bleeding (21,28,30). Given the impressive ability of tamoxifen to stop an episode of bleeding and to reduce total bleeding days in users of the LNG implant, it is promising that tamoxifen may have a similar ability to reduce irregular bleeding in users of the LNG-IUS. Developing tamoxifen for this new indication would be a benefit to women and clinicians managing this common contraceptive side effect.

This project will address whether administration of a short course (seven days) of tamoxifen can reduce early bleeding/spotting days in users of the LNG-IUS. Similar to the Warner study, study medication will be administered for 7 days starting 21 days after insertion of LNG-IUS, and bleeding outcomes will be assessed for 30 days after treatment.

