Women who enroll in the study will track bleeding and spotting starting on the day after LNG-IUS insertion via response to daily automated text messages. Those who are compliant with text message diaries over the first 14 days (responding 12 or more days, approximately 90% response rate) will be invited by phone to return for study visit 1 (occurring between 14-21 days after IUS insertion). On this scheduling phone call, post-insertion exclusions will be reviewed. Eligible women scheduled for study visit 1 will be randomized by the OHSU research pharmacy on the day prior to their scheduled visit. We anticipate that ensuring compliance with preliminary data collection will help minimize loss to follow up or missing data after randomization. The baseline bleeding data may be used as a covariate in final analysis.

The OHSU research pharmacy will randomize subjects to tamoxifen or placebo through a computer-generated algorithm using a block size of six. Treatment allocation will be double-blinded and study investigators will not have access to the randomization scheme or treatment assignments. The research pharmacy will maintain allocation concealment until completion of the study. Study drug (oral tamoxifen 10mg) will be purchased and routed through the OHSU research pharmacy, and identical placebo will be compounded by the research pharmacy. At

study visit 1, each subject will receive a total of seven days of medication to take home (14 pills). They will be instructed to start this medication on day 21 after insertion of their LNG-IUS.

Women with inadequate responses to the text message diary (less than 12 of 14 days) during the 14-day observation period will be contacted by phone to confirm discontinuation from the study, and they will stop receiving automated text messages.

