1.3.7 Follow-up procedure

Bleeding diaries

The primary outcome variable of this study is the total number of bleeding/spotting days over 30 days, but other bleeding outcomes including duration of bleeding-free episodes and frequency of bleeding episodes will be assessed as secondary outcomes. In order to collect bleeding data, all subjects will be asked to complete both paper and electronic bleeding diaries. For the electronic bleeding diary, after initial enrollment, participants will start receiving a daily text or email message from a study-affiliated messaging service (developed with Mir3, San Diego, CA) prompting a response about their bleeding for the day. Subjects can indicate at enrollment whether they want to receive the message via text or email. This approach using the

same service provider has been previously used by our group and others with excellent real-time response rates (>90%) (33). The text message/email bleeding diary for this project was uniquely designed by OHSU and Mir3 to fit the needs of this study. Subject ID numbers and their cell phone numbers or email addresses are entered into the system to allow subjects to receive messages and send responses to the study database. The company adheres to a strict privacy policy for phone numbers in the system, which is detailed in section 1.3.10. In the daily text or email message, subjects are asked to classify their bleeding using the terminology recommended by Mishell et al (32). This includes for a given 24-hour period whether the woman has experienced:

1. Bleeding – any day during which bleeding requires the use of protection with a tampon, pad or panty liner.
2. Spotting – Minimal blood loss that does not require the use of any protection including panty liners (Use of precautionary liners does not qualify as spotting).
3. No bleeding

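### The 30-day count has no rule for diaries cut short, so early leavers can score falsely low on the primary outcome

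*Combined protocol and SAP*

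**What the plan says.** Section 1.3.7: "The primary outcome variable of this study is the total number of bleeding/spotting days over 30 days". Section 1.3.11 derives it directly from the diary ("From these diaries, counts of total bleeding/spotting days will be obtained") and compares group means with a two-sided t-test, by intention to treat, with non-parametric methods if the data are very skewed.

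Section 1.3.9 ends participation at IUS removal and says of withdrawal: "No further data will be obtained from the patient once withdrawal occurs". It then states, both for withdrawal and for loss of contact: "Any data obtained up to this point will be analyzed in accordance with intention to treat".

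Section 1.3.2 enrols 21 women per group to allow for 20% dropout. Section 1.6 gives the reason: "our sample size was designed to account for a 20% dropout rate due to this risk of poor retention in women experiencing ongoing bleeding". It also notes: "Similar prior studies in the LNG-IUS had low dropout rates, all with <20% loss to follow up".

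Section 1.3.4 sets the randomisation time: "Eligible women scheduled for study visit 1 will be randomized by the OHSU research pharmacy on the day prior to their scheduled visit". That visit falls 14-21 days after insertion and study drug starts on day 21, so a randomised woman can leave before the window opens.

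**The concern.** An outcome that needs 30 days is applied to women with fewer, and nothing converts one to the other. A woman who bleeds on all 15 observed days and then has her IUS removed scores 15, below the placebo mean of 18 expected in 1.3.2. A poor course looks better than average.

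The missing days are unlikely to be unrelated to the outcome, because 1.6 ties poor retention to ongoing bleeding. If tamoxifen works, placebo may lose more women and its total falls more, so a real benefit is understated. The reverse split would overstate it. Women with no window day at all are also unaddressed.

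**Working it through.** **1. Is there a scoring rule elsewhere?** No.
- The 12-of-14-day requirement in 1.3.4 applies only before randomisation.
- The repeat message and paper diary (1.3.7) and the call after three silent days (1.3.9) reduce missing days but do not score them.
- Section 1.6 refers to 1.3.7 for handling loss to follow-up, but 1.3.7 covers only collection and reminders.

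**2. The plan's own sample size.** Inputs from 1.3.2: difference 7 days, SD 7, two-sided 0.05, power 80%. The standardised difference is 7/7 = 1. The t-test needs 16.7, so 17 per arm. 17 x 1.2 = 20.4, so 21 per arm and 42 in all, which matches the plan. (Dividing 17 by 0.8 gives 22 per arm.) Adding women to replace leavers treats leavers as supplying no outcome, whereas 1.3.9 keeps their data. The two do not match.

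**3. Expected plain count.** Inputs: placebo mean 18; tamoxifen mean 18 x 0.6 = 10.8; true difference 7.2. Assumed: a fraction d of an arm leaves, on average halfway through the window. Expected count = mean x (1 - d/2). Loss is written placebo/tamoxifen.
- 10%/10%: 17.10 - 10.26 = 6.84
- 20%/20%: 16.20 - 9.72 = 6.48
- 20%/12.2%: 16.20 - 10.14 = 6.06
- 20%/4.4%: 16.20 - 10.56 = 5.64
- 10%/30%: 17.10 - 9.18 = 7.92

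The unequal splits use the implant study in 1.1.1, where "there were fewer discontinuations due to bleeding over the course of the study (2 vs 9", tamoxifen first. Applied to all loss, 20% x 2/9 = 4.4%. Applied to half of the placebo loss, with the other half equal in both arms, 10% + 10% x 2/9 = 12.2%. The 10%/30% split only shows the opposite direction.

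**4. Power.** Simulation with 21 per arm and SD 7. Each woman's daily bleeding probability is drawn from a beta distribution, the leaving day is uniform over the window and independent of bleeding, and the test is a two-sided t-test (12,000-20,000 replicates). With complete diaries: 7.2 days, 89% power.

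| Loss | Plain count | Leavers left out | Per observed day x 30 |
|---|---|---|---|
| 10%/10% | 6.8 days, 83-84% | 7.2, 85% | 7.2, 88% |
| 20%/20% | 6.5, 77-78% | 7.2, 80-81% | 7.2, 87% |
| 20%/12.2% | about 6.0, 72-73% | not run | 7.2, 87% |
| 20%/4.4% | 5.6-5.7, 66-67% | 7.2, 84% | 7.2, 88% |
| 10%/30% | 7.9, 93% | not run | 7.2, 87% |

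**5. No true effect.** The plain count keeps type I error at 5% under 20%/20%. At 20%/5% the expected false difference is 16.20 - 17.55 = -1.35 days (tamoxifen looks worse) and type I error is about 9%. The scaled value stays at about 5% in both cases.

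**The case against.** The strongest reply is that the harm depends on one reading. The plan never says that an unobserved day counts as zero, and a reader who infers that goes beyond the text. Section 1.3.2 supports leaving dropouts out; under the assumptions in step 4 that gives no bias and 80-81% power at 20%/20%, which is what was planned. This stands as far as it goes: the plan supports two readings, and the plain count is only one of them. But leaving women out does not fit 1.3.9, which says twice that their data are analysed.

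The size is also open to challenge. Under equal loss the plain count stays close to plan: 83-84% at 10%/10%, and about 2-3 points below 80% at 20%/20%. The 2 vs 9 figure counts bleeding discontinuations among implant users who already complained of bleeding and were followed for 90 days, and 1.1.1 gives no denominators. Applying it to all loss in a 30-day prevention trial is an extreme case. At 10% placebo loss with half of it bleeding-related (10%/6.1%), the plain count gives 6.6-6.7 days and 81-82% power. The run-in requirement, repeat messages, paper backup, daily payment, follow-up calls and short duration make 20% an upper end. All of this stands, and it limits the size of the problem. It does not supply a rule.

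**Conclusion.** The concern holds as a gap with a cheap remedy. The primary outcome, the retention rule in 1.3.9 and the sample-size basis in 1.3.2 do not say the same thing about women who leave. Following 1.3.9 and 1.3.11 literally gives those women falsely low counts.

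Against a true 7.2 days, the estimate under the plain count is about 6.5-6.8 days with equal loss of 10-20%, and about 6.0 days at 20%/12%. The 5.6-5.7 days and 66-67% power at 20%/4.4% mark an extreme and are not a forecast. All loss rates, splits and leaving times are assumptions.

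Three stronger conclusions are not supported:
- **The trial is underpowered as planned.** Its sample size reproduces, and leaving dropouts out meets the target at 20% equal loss.
- **The false-positive rate is inflated.** That needs unequal loss without a drug effect, for which the documents give no cause.
- **The bias always runs against tamoxifen.** The direction follows the split. However, 1.3.5 reports rare side effects that did not differ between arms, so heavier loss on tamoxifen is not what the plan leads one to expect.

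**What to change.** In 1.3.11:
- Define the primary value as bleeding/spotting days divided by observed diary days in the 30-day window, times 30, for every randomised woman with any window data, compared by the planned test. The same denominator handles isolated unreported days.
- Leave any minimum number of observed days to the investigators, fixed before unblinding. A minimum protects against very short diaries but drops early leavers whom 1.3.9 keeps.
- List women with no window day by arm with their reason for leaving, and report observed days by arm.
- Add one sensitivity analysis that scores the remaining window days as bleeding/spotting for women whose IUS is removed for bleeding after day 21. Restricting it to removals after day 21 avoids giving 30 of 30 days to a woman who left before any study drug.
- State in 1.3.2 or 1.3.9 how the 20% allowance relates to this analysis set.

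The cost is a few sentences and one extra analysis. The drawback is that scaling assumes unobserved days resemble observed ones. If the drug effect starts only after the first week, the scaled estimate without a minimum falls short by about 0.6-0.8 day at 20%/20% (80-81% power, against 78-79% for the plain count). In that case leaving dropouts out does better (7.2 days, 83-84%). Scaling can also mislead if bleeding drives leaving; the sensitivity analysis shows how far the result depends on that.
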